## 1.0 PROTOCOL SUMMARY AND/OR SCHEMA

Purpose:	The objective of this study is to evaluate hepatic arterial embolization for hepatocellular cancer using microscopic beads and the same microscopic beads loaded with doxorubicin.
Study design:	Single center, single blind, prospective, randomized phase II controlled, to be conducted without crossover with patients recruited over a 2 year period
Study agents:	Biocompatibles LC Bead ( Beads + doxorubicin ), 100-300 microns, 150 mg doxorubicin per procedure with additional 100-300 micron and larger size beads (Bead Block) as necessary to achieve stasis  Bead Block ( Beads ) microsphere, 100-300 micron with additional larger size beads as necessary to achieve stasis
Limitations of Study	LC Bead and Bead Block are both tinted blue. Because doxorubicin is red, the addition of doxorubicin to the embolization microspheres will change the color of the spheres to some degree, and thus it may be possible for the interventional radiologist performing the embolization to differentiate between the two embolics. All other participants performing image and data analysis will be blinded.
Enrollment:	100 patients will be enrolled, 50 in each study arm
Clinical site:	Memorial Sloan-Kettering Cancer Center, NY, NY
Primary endpoint:	Response to treatment by RECIST criteria
Secondary endpoints:	

• Tumor necrosis

• Toxicity

• Time to progression

• Survival

Safety endpoint:	The safety endpoint will be treatment related Serious Adverse Event (SAE) rate, defined by SAE occurring within 30 days of a procedure. SAE is defined as a grade 3 or 4 adverse event using the Common Terminology Criteria for Adverse Events (CTCAE) 3.0.
Primary analysis:	Intent-to-treat analysis
Secondary Analysis:	Per protocol analysis and treated population analysis
Principle Investigator:	[name]

Member  
Department of Radiology  
Memorial Sloan-Kettering Cancer Center  
[name]  
[name]

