### **6.2 Subject Exclusion Criteria**

1. Patient has another primary tumor, with the exception of conventional basal cell CA, superficial bladder cancer, melanoma in situ, or treated prostate cancer currently without biochemical or radiographic evidence of active disease.
2. Women who are pregnant or lactating
3. Patient previously treated with doxorubicin
4. Contraindication to angiography/embolization including:

- a. Patients who cannot receive contrast
  - i. Severe allergic reaction to contrast despite pre-medication
  - ii. Poor renal function
- b. Lack of arterial access (e.g. femoral artery occlusion)
- c. other, based on judgment of the investigator
5. Patient has already undergone hepatic arterial embolization for the hepatocellular cancer for which they are currently being evaluated.
6. Patient has received prior radiotherapy for the hepatocellular cancer for which they are currently being evaluated.
7. Patient has had previous local-regional treatment of the current target tumor volume.
8. Patient who cannot have CT scan
9. Patient at very high risk for post-embolization hepatic failure
  - a. Child's C cirrhosis
  - b. >75% liver replaced by tumor
10. Cardiac exclusion for:
  - a. Myocardial infarction within 90 days of study
  - b. Uncontrolled arrhythmia
  - c. LVEF < 50%, for patients randomized to receive LC Bead
11. Patients with tumors exhibiting characteristics considered contra-indications to particle embolization, including:
  - a. Collateral vessel pathways potentially endangering normal territories during embolization
  - b. Arteries supplying tumor not large enough to accept LC Bead or Bead Block
  - c. Presence of arterial to systemic venous shunts
  - d. Presence of arterial to pulmonary vascular shunts

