## 8.0 PRETREATMENT EVALUATION

### Day – 6 weeks

Within 6 weeks of registration, patients will be seen by a hepatobiliary surgeon, GI oncologist, or interventional radiologist and, if general criteria for the study are met, he/she will have a triple phase CT. They will have vital signs (weight, blood pressure, temperature, heart rate) checked. After review of the CT, informed consent will be obtained by the interventional radiologist PI or Co-I, and the patient will be randomized. This will allow for stratification into patients whose treatment is expected to be complete after one embolization procedure, and those who will need two embolization procedures to complete their first treatment. Patients randomized to the LC

Bead (Bead + Dox) group will also have a cardiac echo or a MUGA scan to determine baseline ejection fraction (EF) if they have not had an evaluation of their EF within 3 months.

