## 10.0 EVALUATION DURING TREATMENT/INTERVENTION

Time line	Within 6 weeks	Within 4 weeks	Within 2 weeks 	Time 0	Day 1	10-14 Days	Within 2-3 weeks	10-14 weeks	5-6 months	8-9 months	11-12 months
Clinic Visit 	X		X				X 	X	X	X	X
Laboratory tests											
CBC		X	X		X	X 	X	X	X	X	X
PT, INR, PTT		X	X				X	X	X	X	X
electrolytes		X	X				X	X	X	X	X
BUN/creatinine		X	X				X	X	X	X	X
AFP		X	X				X	X	X	X	X
Albumin, total protein, bilirubin (total)			X	X			X	X	X	X	X
LDH, Alk. Phosphatase, ALT, AST			X	X			X	X	X	X	X
Hepatitis screening (B and C)			X 								
Radio logic tests											
Triple phase CT (TPCT)	X						X 	X 	X 	X 	X 
Treatment											
Hepatic Embolization procedure				X 							
Others											
ECG		X									
MUGA scan or Cardiac Echo			X 								
ECOG assessment								X	X	X	X
Vital Signs checked	X		X				X	X	X	X	X

For patients randomized to the LC Bead (particle + doxorubicin) group. Patients will have repeat MUGA scan or cardiac echo after every 3 treatments, or 450 mg of doxorubicin, and prior to exiting protocol if feasible. If patient exits protocol unexpectedly (e.g. due to death), no MUGA scan or cardiac echo is necessary.

Only for patients who require 2 embolizations to complete one treatment, within 2 weeks of the second embolization the patient will return for clinic, vitals and laboratory tests.

Time 0 is the day of the patient's completed treatment, either single or two embolizations sessions, as anticipated by pre-treatment CT.

CBC may be done locally.

CT used to determine response to treatment.

CT used to determine the need for re-treatment.

If there is evidence of disease progression; a repeat treatment will be scheduled within 2 months  $\pm$  2 weeks. The patients will be re-treated with the same embolic agent used in the first treatment. Patients will not receive more than 450 mg of doxorubicin per annum. They will then re-enter the follow-up pathway.

 Clinic visit will include recording of vital signs, ECOG status and assessment of any SAE

 No ECOG assessment will be done at 2-3 weeks post embolization visit since patients might still be experiencing post-embolization syndrome

If not already done.

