## **13.0 CRITERIA FOR REMOVAL FROM STUDY**

If the patient develops < 5% necrosis by volume following the initial treatment, or increase of >50% in sum of uni-dimensional measurements following subsequent treatments he/she will be considered a treatment failure and will be taken off study and referred for alternative therapy.

If at any time the patient develops unacceptable toxicity he/she will be removed from study.

Known or suspected pregnancy will result in withdrawal of patient from study.

If at anytime the patient is found to be ineligible for the protocol as designated in the section on Criteria for Patient/Subject Eligibility (i.e., a change in diagnosis or condition), including an LVEF of <50%, the patient will be removed from the study.

Non-compliance, patient preference.

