#### Data Needing to be Entered:

- The date the adverse event occurred
- The adverse event
- Relationship of the adverse event to the treatment (drug, device, or intervention)
- If the AE was expected
- The severity of the AE
- The intervention
- Detailed text that includes the following information:
  - A explanation of how the AE was handled
  - A description of the subject's condition

- Indication if the subject remains on the study
- If an amendment will need to be made to the protocol and/or consent form

The PI's signature and the date it was signed are required on the completed report.

For IND/IDE protocols:

Only UADEs and patient deaths will be reported to the FDA as they occur. For these reports, The CRDB AE report should be completed as above and the FDA assigned IND/IDE number written at the top of the report. If appropriate, the report will be forwarded to the FDA by the SAE staff through the IND Office. **All other SAEs will be recorded as part of the study's data and will be included in the study's progress reports to the FDA.**

This study will collect all SAEs that occur from date of consent until the patient is off study. Since elevation in liver function tests is expected in the immediate post treatment period, no elevation in liver function tests occurring within 2 weeks following treatment will be reported as an SAE, although all elevations will be recorded and captured among the data for the study. The following is a list of the liver function tests: Alkaline Phosphatase, ALT, AST, and Bilirubin. All other elevations to Grade 3 or 4, along with any hospitalization will be reported as SAEs and only reported to the FDA as they occur if considered an UADE.

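### Ineligibility found after randomization removes the patient from the study, not only from treatment, so SAE collection can end before the 30-day safety window closes and other outcomes are left without a rule

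*Combined protocol and SAP*

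**What the plan says.** Section 6.0 applies the eligibility criteria at entry and again before each treatment, so they keep operating after randomization. Section 13.0 gives the consequence when they fail: "i.e., a change in diagnosis or condition), including an LVEF of <50%, the patient will be removed from the study".

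On safety, Section 1.0 sets the endpoint as the treatment-related SAE rate, "defined by SAE occurring within 30 days of a procedure". Section 17.2 sets the collection period: "This study will collect all SAEs that occur from date of consent until the patient is off study". It adds that "no elevation in liver function tests occurring within 2 weeks following treatment will be reported as an SAE", but also says that all such elevations are still recorded in the study data.

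On cardiac function, the exclusion in Section 6.2 reads "LVEF < 50%, for patients randomized to receive LC Bead". Section 8.0 describes the baseline EF test after randomization, for that arm only, and "if they have not had an evaluation of their EF within 3 months". Footnote 1 to the Section 10.0 schedule, again for that arm only, says "Patients will have repeat MUGA scan or cardiac echo after every 3 treatments, or 450 mg of doxorubicin".

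On analysis, Section 1.0 names the primary analysis as "Intent-to-treat analysis". Response is read from one CT, 2-3 weeks after the first complete treatment (Sections 4.1 and 10.0). Section 14.0 plans Kaplan-Meier and log-rank analyses of time to progression (TTP) and survival.

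**The concern.** Stopping embolization in a patient who no longer qualifies is correct care. The difficulty is that the plan has one exit for two different events, stopping treatment and stopping observation.

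The criteria re-checked before each treatment include ECOG 0-1, Okuda stage I or II, bilirubin below 3 mg/dl and absence of Child's C cirrhosis. Section 11.0 lists deterioration of liver function, up to frank liver failure, as a risk of embolization. The removal rule can therefore act on patients whom the procedure has harmed, which is when the safety endpoint most needs complete data.

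One trigger, low LVEF, can be detected in only one arm. The named primary analysis keeps all randomized patients, but the plan does not say what response a patient without the response CT is given.

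**Working it through.** **1. What removal means.** Section 13.0 does not distinguish leaving treatment from leaving the study, and no other section does so. Read literally with Section 17.2, SAE collection ends on the day of removal.

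**2. When removal can fall inside the 30-day window.** If the last procedure is on day 0 and removal on day d, the uncollected part is max(0, 30 − d) days.

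- *Before any embolization* (for example, a low baseline EF): there is no procedure, so no window is lost.
- *Between two sessions of one treatment* (Section 9.0): the second session is planned 2 to 6 weeks after the first, day 14 to day 42, and eligibility applies before it.
  - d = 14: 30 − 14 = 16 days lost, 16/30 = 53%.
  - d = 21: 30 − 21 = 9 days lost, 9/30 = 30%.
  - d = 30 to 42: 0 days lost.
  - The clinic visit with laboratory tests falls within 2 weeks of the second session. A removal prompted by that visit can come before the planned session day, and the loss is then larger.
- *Before re-treatment*: re-treatment is decided on the 10-14 week CT at the earliest. 10 weeks is 70 days, which is past 30, so nothing is lost for the earlier procedure.
- *Repeat EF*: due after three treatments or 450 mg, with no stated interval from the procedure. If it is done within 30 days of that procedure and LVEF is below 50%, the window is cut short, in the Bead + Dox arm only.
- *Unscheduled*: Section 13.0 applies at any time, so removal on any other day is possible.

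**3. The one-arm route.** Section 13.0 names LVEF without naming an arm. The asymmetry follows from Sections 6.2, 8.0 and 10.0: the criterion, the baseline test and the repeat test all belong to patients assigned to LC Bead. Assignment is generated at registration (Section 15.2). The eligibility check at registration therefore cannot settle this criterion unless a recent EF is already on file.

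**4. Response rate.** The plan's own precision comes first: 1.96 × √(0.5 × 0.5 / 50) = 0.139, which reproduces the stated ±14%. With k patients in an arm removed before the response CT, the rate is undetermined over a range of k/50:

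| k | k/50 |
|---|---|
| 1 | 2 points |
| 3 | 6 points |
| 5 | 10 points |

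The documents give no value for k. Only removals before that CT matter here: a low baseline EF, a disqualifying finding at the first angiogram, or ineligibility before a planned second session. The repeat EF comes too late. Three procedures at 150 mg make 450 mg, and the first treatment uses at most two (300 mg), so the third is a re-treatment after the response CT.

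**5. TTP and survival.** Section 12.0 repeats measurements at each imaging for the duration of the study. Section 10.0 sets out CT beyond 11-12 months for patients with CR or SD, until death or progression. Section 14.0 assumes a median follow-up of 3 years with about half of patients dying. None of these says what happens after removal for ineligibility, or how such patients enter the Kaplan-Meier analysis. Any bias figure would need a removal fraction, a hazard after removal and a censoring rule. The documents give none of these, so no figure is computed.

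**The case against.** The strongest case is that the affected group is small and part of the loss is inferred from silence. Most of this stands, and it limits the point.

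- *A reader might infer that the 2-3 week visit is where safety data are generally lost.* The documents do not support that. Scheduled eligibility checks precede treatments, and the removal rule tied to the result of the first post-treatment CT is treatment failure on necrosis, a different route. A removal for ineligibility at that visit is possible but is not the planned sequence.
- *A reader might infer that liver events largely vanish*, because early elevations are not reported as SAEs and later ones can be cut off. Section 17.2 records all the early elevations as data, and whether the endpoint follows the reporting exemption is not stated.
- *A reader might infer that removed patients are lost for survival, so that its estimate is biased upward.* No section says that survival follow-up stops at removal or that censoring occurs then. The 3-year assumption suggests that survival is meant to be tracked, and vital status needs no study visit. What is missing is the rule. Section 14.0 also treats this aim as preliminary data for a later trial.
- *Intent-to-treat is already named.* It fixes who is in the denominator, but supplies neither an outcome for a patient without the CT nor SAEs after collection has ended.
- *Time to treatment failure* counts discontinuation for any reason, so it is largely unaffected.

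The mismatch between the 30-day endpoint and the collection rule is not answered by any of this.

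**Conclusion.** The point holds and should be corrected. Followed as written, Sections 13.0 and 17.2 can shorten the safety window that Section 1.0 defines, chiefly for a patient who becomes ineligible between two sessions. The loss is 16 of 30 days for removal at day 14, falling to none from day 30. This rests on taking removal from the study to mean being off study, which is the plain reading.

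The LVEF route exists in the Bead + Dox arm only. For the primary endpoint it matters only through a low baseline EF. Each patient in either arm who is removed before the response CT leaves 2 points of that arm's rate undefined, against a stated precision of ±14%. The number of such patients is not given and may be small.

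For TTP and survival the finding is an absent rule. The documents do not show that data will be lost, and they do not allow the size of any bias to be estimated.

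**What to change.** 1. **Section 17.2:** collect SAEs for at least 30 days after the last procedure, even if the patient is off study treatment.
2. **Section 13.0:** state that ineligibility after randomization stops study treatment only. Continue survival follow-up until death. Continue scheduled CT until progression where it is safe and still relevant, so not in pregnancy, with a contraindication to contrast or CT, or after a changed diagnosis. Both apply unless the patient withdraws consent.
3. **Sections 1.0 and 14.0:** keep all randomized patients in the primary denominator, count those without a response CT as non-responders, and report removals by arm and reason.

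Two additions are not recommended. A sensitivity analysis leaving out LVEF removals would drop low-EF patients from one arm and keep them in the other. EF testing of everyone before randomization would remove the baseline asymmetry, but needs extra procedures in patients who will not receive doxorubicin.

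**Cost:** text changes in four sections and follow-up of a few more patients, with no change in sample size. The non-responder rule lowers the response rate slightly, mainly in the Bead + Dox arm, because control patients with low EF are treated and counted normally. With an assumed 30% response among the remaining patients, that arm would read 0.30 × 49/50 = 29.4% with one LVEF removal and 0.30 × 45/50 = 27.0% with five. Reporting removals by arm and reason lets a reader see this effect.

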## **6.0 CRITERIA FOR SUBJECT ELIGIBILITY**

Patients will be eligible for the study if they fulfill the following criteria at entry and prior to each treatment

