## **15.0 RESEARCH PARTICIPANT REGISTRATION AND RANDOMIZATION PROCEDURES**

### **15.1 Research Participant Registration**

Confirm eligibility as defined in the section entitled Criteria for Patient/Subject Eligibility.

Obtain informed consent, by following procedures defined in section entitled Informed Consent Procedures.

During the registration process registering individuals will be required to complete a protocol specific Eligibility Checklist.

All participants must be registered through the Protocol Participant Registration (PPR) Office at Memorial Sloan-Kettering Cancer Center. PPR is available Monday through Friday from 8:30am – 5:30pm at [contact]. The PPR fax numbers are [contact] and [contact]. Registrations can be phoned in or faxed. The completed signature page of the written consent/verbal script and a completed Eligibility Checklist must be faxed to PPR.

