### **15.2 Randomization**

Randomization will be performed using the Clinical Research Database (CRDB), the central computing facility for clinical research at MSKCC. This system will generate a treatment assignment using the method of permuted blocks, at the time the patient is registered. Due to the nature of the treatment, the interventional radiologist may not be blinded but the radiologists assessing response to treatment will be blinded to treatment assignment.

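### LVEF below 50% removes patients from the study after randomisation in the Bead + Dox arm only, which conflicts with the intent-to-treat analysis; the effect is probably small and the fix is cheap

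*Combined protocol and SAP*

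**What the plan says.** The relevant rules are spread over several sections of the combined protocol and SAP.

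- **Exclusion by arm.** Section 6.2, item 10c: "LVEF < 50%, for patients randomized to receive LC Bead". Items 10a and 10b (recent infarction, uncontrolled arrhythmia) apply to both arms.
- **Order of events.** Section 15.1 starts registration with "Confirm eligibility as defined in the section entitled Criteria for Patient/Subject Eligibility". Section 15.2 adds: "This system will generate a treatment assignment using the method of permuted blocks, at the time the patient is registered". Section 8.0 has the same order: after the CT is reviewed, "informed consent will be obtained by the interventional radiologist PI or Co-I, and the patient will be randomized".
- **Who is tested.** Section 8.0 then asks for an echo or MUGA in the Bead + Dox group, unless an ejection fraction from the previous 3 months exists. Section 10.0 (footnote 1) and Section 17.0 also confine cardiac testing to the LC Bead group.
- **Consequence.** Section 13.0, on patients found ineligible: "including an LVEF of <50%, the patient will be removed from the study". Section 6.0 applies the criteria more than once: "Patients will be eligible for the study if they fulfill the following criteria at entry and prior to each treatment".
- **Analyses.** Section 1.0 makes intent-to-treat the primary analysis and lists as secondary "Per protocol analysis and treated population analysis", without defining either set. Section 14.0 compares TTP and survival between groups by the log-rank test.

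**The concern.** An exclusion that depends on the allocated arm cannot be fully settled before allocation. Take two patients with the same LVEF, say 45%. The one allocated to Bead + Dox is tested and removed from the study. The one allocated to Bead has no scheduled test, is embolized and stays. Only the allocation differs.

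Three planned analyses are touched.

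1. **Primary response.** A patient removed at baseline has no CT at 2-3 weeks after treatment. Intent-to-treat needs a result for that patient, and the plan gives no rule for one.
2. **TTP and survival.** Section 4.1 starts the clock for local progression at randomisation. No section continues follow-up after removal, so these patients can drop out of the log-rank comparison in one arm only.
3. **Treated and per-protocol sets.** On the natural reading, a patient removed before embolization is in neither set. Bead + Dox would then be screened on LVEF and Bead would not. The analyst could not match the arms afterwards, because LVEF is not systematically collected in Bead.

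Section 14.0 explains that the trial is randomised because control data were insufficient. Section 3.0 says a response difference, coupled with a gain in TTP or survival, might be the basis for a phase III trial. The comparability of the arms therefore matters, even though the stated aim is estimation.

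**Working it through.** **Inputs from the documents:** 50 patients per arm and precision +/- 14% (Section 14.0); 2-year survival 68% after embolization at this centre (Section 3.0, Preliminary Data).

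**Assumed, because the documents give no figure:** share q with LVEF below 50%, 2% to 10%; true response rate 30%; for the survival illustration, a death rate h = 2 to 3 times higher in low-LVEF patients.

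**Step 1: the plan's own figure.** The 95% half-width at p = 0.5 (level assumed) is 1.96 x sqrt(0.25/50) = 0.1386, so the stated +/- 14% reproduces. For a difference between arms it is 1.96 x sqrt(2 x 0.25/50) = 0.196, about 20 points.

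**Step 2: how many patients.** Expected removals k = 50q. The chance of at least one is 1 - (1 - q)^50.

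**Step 3: intent-to-treat response with removals counted as non-response.** Rate = 0.30 x (50 - k)/50. The span between none and all of the removed responding is k/50.

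| q | Expected removals k | Chance of at least one | Response rate | Fall from 30% | Span k/50 |
|---|---|---|---|---|---|
| 2% | 1 | 63.6% | 29.4% | 0.6 points | 2 points |
| 5% | 2.5 | 92.3% | 28.5% | 1.5 points | 5 points |
| 10% | 5 | 99.5% | 27.0% | 3.0 points | 10 points |

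So at least one such patient is likely across the assumed range, but the shift in the rate is small against 14 points.

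**Step 4: treated or per-protocol set, if removed patients are dropped.** Bead + Dox falls to 50(1 - q) = 49, 47.5 or 45 patients, with half-widths of 14.0%, 14.2% and 14.6%; Bead stays at 50. The Bead + Dox rate shifts by q x (outcome gap between patients above and below the limit). A gap of 10 to 40 points (assumed) gives 0.02 x 10 = 0.2 to 0.10 x 40 = 4 points. Nothing in the documents shows that such a gap exists for RECIST response.

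**Step 5: survival, if removed patients are also not followed.** Let s be the 2-year survival of screened patients. Solve (1 - q)s + q s^h = 0.68, with no drug effect.

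- q = 2%, h = 2: s = 68.4%; apparent hazard ratio 0.98.
- q = 10%, h = 3: s = 71.5%; apparent hazard ratio 0.88.

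The hazard ratios are events per person-time over 3 years with exponential survival. For the second case, the screened hazard is -ln(0.715)/2 = 0.168 per year. The mixed arm has 0.9 x 0.395 + 0.1 x 0.779 = 0.434 events in 0.9 x 2.36 + 0.1 x 1.55 = 2.28 person-years, or 0.191 per year; 0.168/0.191 = 0.88.

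**Step 6: repeat tests.** The scheduled repeat comes after every 3 treatments or 450 mg. A first treatment delivers at most 300 mg (Section 9.0), and the response CT follows 2-3 weeks later. The scheduled repeat therefore falls after the primary assessment.

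**The case against.** Only one arm receives a cardiotoxic drug, so testing only that arm has a clear safety reason. The trial estimates response rates, and Section 14.0 describes the survival aim as preliminary data for a later trial. Recent infarction and uncontrolled arrhythmia are excluded in both arms and ECOG must be 0 or 1, which may make low LVEF uncommon. Silence on follow-up after removal covers every reason in Section 13.0, not LVEF alone.

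Much of this stands. The safety reason justifies withholding LC Bead; it does not require ending study participation. The silence on follow-up is general, but the baseline LVEF removal can arise by rule in one arm only.

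A reader might infer more than the documents support:

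- **That the primary result is biased.** Counting a randomised patient who cannot receive doxorubicin as a non-responder is ordinary intent-to-treat. What is missing is the rule, together with a removal clause that works against it.
- **That the treated and per-protocol sets certainly exclude these patients.** The sets are named but not defined. Exclusion is the natural reading and not a stated rule.
- **That LVEF is never measured in Bead.** It is not scheduled. Some Bead patients may have a value from routine care, and some Bead + Dox values may pre-date randomisation because a result from the previous 3 months is accepted.
- **That later removals are the same selection.** Those patients have been treated and stay in a treated set, and a later fall in LVEF may be doxorubicin toxicity. Section 6.0 reapplies the criteria before each treatment but schedules no LVEF test there.

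**Conclusion.** The point holds as a limited one. The protocol writes down a removal after randomisation that can act at baseline in Bead + Dox only. It conflicts with the planned intent-to-treat analysis, can enter the TTP and survival comparison, and would leave any treated or per-protocol set LVEF-screened in one arm. I found no other section that corrects this.

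The size is probably small: 1 to 5 of 50 patients and 0.6 to 3 points of response, well inside +/- 14%. That rests on the assumed 2% to 10% share and the assumed 30% rate. The survival illustration needs two further conditions together, that removed patients are not followed and that low LVEF carries 2 to 3 times the death rate; the documents establish neither. The case for acting is that the remedy costs almost nothing, not that the trial's conclusions are at risk.

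**What to change.** **Section 13.0.** State that LVEF below 50% stops LC Bead treatment but not study follow-up, and that TTP and survival continue to be collected in the assigned arm.

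**Section 14.0.** State that:

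- all randomised patients stay in the intent-to-treat analysis;
- patients removed for LVEF before the response CT count as non-responders, with their number reported and the range of the response rate if all of them had responded;
- treated and per-protocol comparisons are labelled as LVEF-screened in Bead + Dox only, and no between-arm conclusion is drawn from them alone.

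**Cost.** A few sentences, continued follow-up of a few patients, and a slightly lower Bead + Dox response rate (0.6 to 3 points under the assumptions above). The treated and per-protocol comparisons remain unmatched on LVEF.

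**Optional, not required.** Testing LVEF in every patient before registration and applying 10c to both arms would remove the imbalance at source. It would add an echo or MUGA in up to about 50 Bead patients without a recent value. It would mean screening about 103 (100/0.98) to 112 (100/0.90) patients to randomise 100, and it would exclude from Bead patients who do not need the cardiac limit.
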